1.2.5. Rationale for Selected Subject Reported Outcome Measures

Subject-based measures of health-related quality of life have increasingly been used by the orthopedic research community as a means to define a successful intervention.¹² Subject reported outcomes typically assessed post-arthroplasty include overall satisfaction with the joint replacement, pain and function.

The Self-Administered Patient Satisfaction Scale (SAPS) will be utilized to assess subject satisfaction in this study. The SAPS is a multidimensional, disease specific measure that evaluates subject satisfaction with the outcome of hip or knee arthroplasty and was designed to be used in conjunction with other clinical measures and functional health status instruments to evaluate the results of hip and knee arthroplasty. The validity and reliability of the scale has been demonstrated.¹³ The scale consists of four items focusing on satisfaction with the extent of pain relief, improvement in ability to perform home or yard work, ability to perform recreational activities and overall satisfaction with joint replacement.

Average pain in the joint to be replaced (pre-surgery) and the replaced joint (post-surgery) will be assessed with an 11-point Numeric Rating Scale (NRS) ranging from zero (no pain) to 10 (worst possible pain). The validity and reliability of the scale has been demonstrated.¹⁴

The functional measures chosen for this study were those which have been shown to be valid, reliable and sensitive and in addition were region-specific and easy to administer. Subjects undergoing total knee or hip replacement will be asked to complete the Western Ontario and McMaster Universities Osteoarthritis Index (WOMAC) with the knee or hip that will be or was replaced serving as the “index joint”. Subjects undergoing total shoulder replacement will be asked to complete the Shoulder Pain and Disability Index (SPADI).

The WOMAC is a self-administered condition-specific instrument which assesses pain, disability and joint stiffness in knee and hip osteoarthritis. It is a valid, reliable and responsive measure of outcome in subjects with arthritis and has been used extensively.^{12,15,16}

The SPADI is a self-administered questionnaire that was developed to measure the pain and disability associated with shoulder pathology in people with shoulder pain of musculoskeletal, neurogenic or undetermined origin. The psychometric properties of the SPADI have been shown to be acceptable for research use and the SPADI has been recommended to assess outcomes in subjects undergoing shoulder arthroplasty.^{17,18} The instrument consists of two dimensions (pain and function). The pain dimension consists of five questions regarding the severity of an individual’s pain. Functional activities are assessed with eight questions designed to measure the degree of difficulty an individual has with various activities of daily living that require upper extremity use.

For each of the selected subject reported outcome measures there are data available in the literature. These data will be utilized to contextualize the results of this study.

1.2.5.1. Interactive Web Response System

To avoid a social desirability bias in the subject reported outcomes, an Interactive Web Response System (IWRS) will be utilized in this study. Contingency plans will be in place to address system and/or connectivity issues with the IWRS.

However, eligibility for this study does not require access to the internet via a desktop, laptop or tablet computer so, for those subjects without access to the internet via a desktop, laptop or tablet computer, paper versions of the assessments will be utilized. Though not optimal, the use of two methods to collect subject reported outcomes will maximize the ability to capture information from all subjects who undergo a total knee, hip, or shoulder replacement surgery while participating in tanezumab Study A4091056, A4091057 or A4091058. Additional considerations which mitigate the concerns about using two methods to collect subject reported outcomes in the same study include that this study has not been formally powered and all analyses will be descriptive rather than inferential.

1.2.6. Summary of Benefit and Risks to Subjects Enrolled in Study A4091064

There is no treatment benefit to subjects participating in Study A4091064 however subjects may derive benefit from the increased post-surgery medical oversight dictated by this study. In addition, information from this study may benefit future patients who receive tanezumab. A detailed discussion of the risks of tanezumab is provided in Section 7 of the Investigator's Brochure. Because no investigational product is administered in Study A4091064, the anticipated investigational product-related risk to subjects participating in Study A4091064 is considered low. However, female subjects who are of childbearing potential and are sexually active and who withdraw from any of the tanezumab studies less than 16 weeks after the last dose of subcutaneous investigational product need to use acceptable methods of contraception due to the potential risk of adverse effects on the fetus if they become pregnant. Finally, although it is considered unlikely given the number of subjects who have been treated with tanezumab to date, it cannot be excluded that some adverse effects of the treatment may become evident after the last administration of the investigational product. The increased post-surgery medical oversight dictated by this study should facilitate recognition of such events if they occur.

Complete information for tanezumab may be found in the Single Reference Safety Document (SRSD), which for this study is the Investigator's Brochure.

2. STUDY OBJECTIVES AND ENDPOINTS

2.1. Primary Objective

- To describe the post-operative outcome of subjects who underwent a total knee, hip, or shoulder replacement while participating in tanezumab Study A4091056, A4091057 or A4091058 (treatment period and safety follow-up period).

2.2. Secondary Objectives

- To compare the post-operative outcome for tanezumab 2.5 mg and 5 mg versus NSAID for subjects who underwent a total knee, hip, or shoulder replacement while participating in tanezumab Study A4091058.
- To describe the post-operative outcome of subjects from the A4091059, A4091061 or A4091063 studies who underwent a total knee, hip, or shoulder replacement.

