1.2.3.1. Overview of Efficacy in Clinical Studies

In the treatment of pain associated with OA, tanezumab monotherapy doses of 2.5 mg to 10 mg have been shown to provide efficacy that is superior to placebo. In addition, tanezumab monotherapy doses of 5 and 10 mg have demonstrated efficacy above that of NSAIDs. Relative to oxycodone, tanezumab monotherapy doses of 5 mg or 10 mg were shown to have a favorable efficacy profile. Tanezumab 10 mg provided minimal additional benefit over tanezumab 5 mg in the treatment of OA.¹¹

In the treatment of CLBP, tanezumab monotherapy doses of 10 mg and 20 mg demonstrated efficacy that was superior to that of placebo and naproxen. Tanezumab 20 mg provided minimal additional benefit over tanezumab 10 mg in the treatment of CLBP.¹¹

The available efficacy data in other chronic pain conditions suggests that tanezumab may provide meaningful analgesia in subjects with neuropathic pain, visceral pain and subjects with pain associated with cancer who have metastatic bone pain.¹¹

Study A4091056 is a randomized, double-blind, placebo-controlled, multicenter, parallel-group, Phase 3 study of the efficacy and safety of tanezumab when administered by SC injection for 16 weeks compared to placebo in subjects with osteoarthritis of the knee or hip. Approximately 690 subjects will be randomized to one of 3 treatment groups in a 1:1:1 ratio. Subjects will receive a total of two SC injections, separated by 8 weeks:

- tanezumab 2.5 mg (Day 1) and tanezumab 2.5 mg (Week 8);
- tanezumab 2.5 mg (Day 1), and tanezumab 5 mg (Week 8);
- placebo to match tanezumab (Day 1) and placebo to match tanezumab (Week 8).

Study A4091056 is designed with a total duration of 40 weeks and will consist of three periods: Screening (37 days), Double-blind Treatment (16 weeks) and Safety Follow-up (24 weeks).

Study A4091057 is a randomized, double-blind, placebo-controlled, multicenter, parallel-group, Phase 3 study of the efficacy and safety of tanezumab when administered by SC injection for 24 weeks compared to placebo in subjects with osteoarthritis of the knee or hip. Approximately 810 subjects will be randomized to one of 3 treatment groups in a 1:1:1 ratio. Subjects will receive a total of three SC injections, separated by 8 weeks:

- tanezumab 2.5 mg;
- tanezumab 5 mg;
- placebo to match tanezumab.

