Study A4091057 is designed with a total duration of 48 weeks and will consist of three periods: Screening (37 days), Double-blind Treatment (24 weeks) and Safety Follow-up (24 weeks).

Study A4091058 is a randomized, double blind, active-controlled, multicenter, parallel-group Phase 3 study of the safety, efficacy, and tolerability of tanezumab when administered by SC injection for 56 weeks compared to NSAIDs in subjects with osteoarthritis of the knee or hip. Approximately 3000 subjects will be randomized to one of 3 treatment groups in a 1:1:1 ratio (N=1000/treatment group). Treatment groups will include:

1. SC placebo (to match tanezumab) once every 8 weeks (a total of 7 administrations) plus naproxen 500 mg BID per os (PO), celecoxib 100 mg BID PO, or diclofenac ER 75 mg BID PO through Week 56.
2. Tanezumab 2.5 mg SC once every 8 weeks (a total of 7 administrations) plus placebo matching naproxen, celecoxib or diclofenac ER to maintain blinded BID oral study treatment administration through Week 56.
3. Tanezumab 5 mg SC once every 8 weeks (a total of 7 administrations) plus placebo matching naproxen, celecoxib or diclofenac ER to maintain blinded BID oral study treatment administration through Week 56.

Study A4091058 is designed with a total duration of 80 weeks and will consist of three periods: Screening (37 days), Double-blind Treatment (56 weeks) and Safety Follow-up (24 weeks).

Study A4091059 is a Phase 3 study of the efficacy and safety of tanezumab in subjects with chronic low back pain, Study A4091061 is a Phase 3 study of the efficacy and safety of tanezumab in cancer patients with pain due to bone metastases. Study A4091063 is a Phase 3 study of the safety and efficacy of tanezumab in Japanese adult subjects with chronic low back pain.

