The most common adverse events reported in the non-controlled, long-term Phase 3 osteoarthritis studies were similar to those seen in the controlled Phase 3 osteoarthritis studies with the exception of the inclusion of musculoskeletal pain and exclusion of hypertension and nasopharyngitis and all gastrointestinal-related adverse events. Dose-related increases in the incidence of peripheral edema, joint swelling, osteoarthritis and paresthesia were observed.

Based on data from the Phase 3 osteoarthritis studies and results of an independent adjudication of investigator-reported adverse events of osteonecrosis and total joint replacements, the risk of rapidly progressive osteoarthritis with tanezumab treatment is greater than with placebo or active comparator treatment.

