1.2.4. Rationale for Study

Measures to better characterize the joint safety issue have been developed and agreed with FDA. This study is one component of the agreed risk characterization measures and is an attempt to address the potential concern that subjects treated with tanezumab have a different post-surgical outcome than those not treated with tanezumab. The total joint replacement data from completed tanezumab studies does not suggest a different post-surgical outcome in tanezumab treated subjects however those data were gathered retrospectively. The types of endpoints to be assessed in this prospective study and the duration of the study have been agreed to with the FDA. Every effort will be made to enroll all A4091056, A4091057 and A4091058 subjects who undergo a qualifying total joint replacement into this study however it is acknowledged that to a certain extent the population enrolled in this study will be 'self-selected' and thus there may be subjects with a qualifying total joint replacement who choose not to enter the study.

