5.3. Safety Analysis Set

The ‘Safety Analysis Set’ (SAS) is the analysis set for all analyses. It consists of all treated subjects who enrolled in Study A4091064, and who have a qualifying total joint replacement for Study A4091064. This analysis set is used in the presentations of all data summaries and listings and is labeled as the ‘Safety Analysis Set’ or ‘SAS’.

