8.2. Statistical Analyses

8.2.1. Analysis of Endpoints

All subjects enrolled in the study who have a qualified total joint replacement will be included in the summary tables. In addition, three types of endpoints, the surgeon’s assessment of procedural difficulty, the subject’s overall satisfaction, and concomitant

nondrug treatment, will be summarized for subjects who were adjudicated with RPOA (type 1 and 2), RPOA (type 1), RPOA (type 2), Primary ON, SIF, or NPOA.

The events considered in the incidence of event summary are total joint replacement and total joint replacement with specific individual or grouped adjudication outcomes, as defined in [Section 8.1.3](#).

Unless otherwise stated, data from this study will be presented at Baseline and Weeks 4, 12, and 24 using observed data (no imputation for missing data), and at Week 24 using Last Observation Carried Forward (LOCF) for missing data. Data will be shown at the timepoints specified and also using change from (pre-surgery) Baseline when Baseline data are available and where relevant. Data will be shown overall, and split by treatment group. Data on surgical difficulty and outcomes, and subject safety data will be summarized by study (if needed), with an additional combined summary for the subjects from the osteoarthritis studies.

For the Surgeon's Assessment of Procedural Difficulty, the number and percentage of subjects in each category (Uneventful, Minor complications, Major complications) will be presented. Complications reported by the surgeon will be listed.

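### The A4091058 tanezumab-versus-NSAID outcome comparison is confined to operated enrollees, so arm differences can reflect case mix and should be shown beside per-treated rates

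*Protocol*

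**What the plan says.** Protocol 2.2, repeated in SAP 2.2, sets this objective for A4091058: "To compare the post-operative outcome for tanezumab 2.5 mg and 5 mg versus NSAID for subjects who underwent a total knee, hip, or shoulder replacement". Protocol 1.2.4 gives the reason for the study as the "potential concern that subjects treated with tanezumab have a different post-surgical outcome than those not treated with tanezumab".

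SAP 5.3 defines the only analysis set: "It consists of all treated subjects who enrolled in Study A4091064, and who have a qualifying total joint replacement for Study A4091064". It adds: "This analysis set is used in the presentations of all data summaries and listings". SAP 8.2.1 then says: "Data will be shown overall, and split by treatment group". SAP 6.3 plans no models and no covariates.

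On how treatment may bear on surgery, Protocol 1.2.3.2 concludes that "the risk of rapidly progressive osteoarthritis with tanezumab treatment is greater than with placebo or active comparator treatment". Protocol 1.2.3.2.2 says that all-cause replacement rates in earlier osteoarthritis studies were comparable across placebo, active comparator and tanezumab monotherapy. Protocol 1.2.4 acknowledges one kind of selection: some subjects with a qualifying replacement may choose not to enter.

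Protocol 9.2 plans, for A4091058, replacement incidence by arm, exposure-adjusted rates, and risk differences and ratios with 95% confidence intervals. SAP 8.1.3 bases its incidence summary on the Safety Analysis Set, and the footnote to SAP 8.2.2 confirms that this means subjects with a replacement who entered A4091064. SAP 8.2.1 adds summaries by adjudicated diagnosis for procedural difficulty, satisfaction and concomitant nondrug treatment.

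**The concern.** Randomisation in A4091058 balances the arms at entry to that study. Having a replacement is a later event. If treatment affects who reaches surgery, when, or with what diagnosis, the operated subjects in each arm are differently selected groups. The contrast between them no longer has the protection of randomisation, even if every eligible subject enrols. Voluntary entry, the only selection the protocol mentions, is a separate problem.

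The stake is how a by-arm table will be read. A gap in complications or satisfaction could be taken as an effect of the drug on surgical outcome when it comes from a different mix of diagnoses. Equally, similar percentages could sit beside different numbers of poor outcomes per patient treated. The planned tables would not let a reader tell these cases apart.

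**Working it through.** There is no power calculation or expected rate by arm to reproduce. The plan's figures are an enrolment ceiling of 250 (Protocol 9.1, no derivation given) and the parent-study sizes. "Approximately 3000 subjects will be randomized to one of 3 treatment groups in a 1:1:1 ratio (N=1000/treatment group") reproduces: 3000/3 = 1000. All risks and shares below are assumptions, and the examples are purely hypothetical.

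**1. Scale and chance error.** The osteoarthritis parent studies total 690 + 810 + 3000 = 4500, so 250 enrollees would be 250/4500 = 5.6%. Spread pro rata, one A4091058 arm has 250 × 1000/4500 = 55.6, about 56. At an assumed 10% risk, the 95% half-width of a difference is 1.96 × √(2 × 0.10 × 0.90/56) = 11.1 points. If all 250 came from A4091058, about 83 per arm, it is 1.96 × √(0.18/83) = 9.1 points. Since 250 is a ceiling, actual numbers may be smaller and the error larger.

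**2. Equal numbers operated, different diagnosis mix.** Let s be the share of operated subjects with rapidly progressive osteoarthritis (RPOA). Complication risk depends on diagnosis only, never on arm. Percentage = (1 − s) × risk in normal progression + s × risk in RPOA. Take s = 10% on NSAID and 30% on tanezumab.

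| Risk, normal progression | Risk, RPOA | NSAID | Tanezumab | Difference (points) |
|---|---|---|---|---|
| 8% | 20% | 7.2 + 2.0 = 9.2% | 5.6 + 6.0 = 11.6% | +2.4 |
| 20% | 8% | 18.0 + 0.8 = 18.8% | 14.0 + 2.4 = 16.4% | −2.4 |
| 15% | 15% | 15.0% | 15.0% | 0 |

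The drug changes nobody's surgical outcome, yet the arms differ in either direction with equal replacement counts. The difference is zero if risks do not depend on diagnosis or if the shares are equal.

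**3. Unequal numbers operated.** Per 1000 subjects in an arm, suppose 40 are operated on under either treatment (risk 10%) and x more only under tanezumab (risk r). Again there is no drug effect on outcome. Tanezumab percentage = (40 × 0.10 + x × r)/(40 + x). With x = 20:

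| r | Tanezumab, per operated | NSAID, per operated | Tanezumab, per 1000 | NSAID, per 1000 |
|---|---|---|---|---|
| 5% | 5/60 = 8.3% | 10.0% | 5 | 4 |
| 10% | 6/60 = 10.0% | 10.0% | 6 | 4 |
| 20% | 8/60 = 13.3% | 10.0% | 8 | 4 |

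In the first row the two measures point in opposite directions. Over x = 10 to 40 and r = 2% to 30%, the operated-only difference runs from −4.0 to +10.0 points. With x = 0 both contrasts vanish.

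**4. Can the planned tables recover the per-treated figure?** Replacement rate × operated-only percentage would give it approximately. In the SAP's set, however, every subject has a replacement, so incidence is n/n = 100% in every arm. The parent-arm denominator of Protocol 9.2 is needed.

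**The case against.** Several points on the other side have force.

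- **The question is conditional on surgery.** Protocol 1.2.4 asks about post-surgical outcome, which exists only for operated subjects. This stands, and the operated-only tables should stay. It does not make the arms comparable within that group.
- **Replacement rates were comparable before.** A reader might infer that the plan will hide harm, with tanezumab looking better per operation and worse per patient treated. The documents do not support that. It needs more replacements on tanezumab, whereas the only statement on rates is that they were comparable. It also needs the extra joints to carry lower surgical risk, and no passage says that joints with RPOA do better after surgery. If they do worse, the operated-only percentage moves against tanezumab. What remains is step 2: equal counts do not guarantee equal case mix.
- **The analyses are descriptive.** The study is called observational, SAP 4.1 and 4.2 rule out inferential testing, and nothing claims a randomised comparison. That removes tests, but the objective still says compare and the tables are still split by arm.
- **Diagnosis is already examined.** SAP 8.1.3 tabulates adjudicated diagnosis by treatment group, which exposes case mix among enrollees. Procedural difficulty and satisfaction are summarised by diagnosis. The nondrug-treatment summary draws on the form that SAP 6.1 uses to derive corrective procedures and rehabilitation. The gap is therefore mainly post-surgical complications, pain and WOMAC.
- **Per-treated rates have their own flaw.** Non-enrolled replacements have no outcome data. If non-enrolment differs by arm, the per-treated contrast is biased in an unknown direction, and calling each rate a lower bound does not disclose that. This is correct, and the fix has to deal with it.

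**Conclusion.** The point holds in limited form. The A4091058 arm comparison conditions on a post-randomisation event whose cause and case mix tanezumab may affect, with no adjustment and no parent-arm denominator in the SAP. Differences between arms can arise from case mix alone and may differ in sign from the burden per treated subject.

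Neither size nor direction can be derived from the documents. The bias is zero if treatment does not change who is operated on or why, or if the added or substituted cases carry the same risk. Chance error of about 11 points either way, under the pro rata and 10% assumptions, exceeds most of the hypothetical differences. A reader might infer that the safety question will be answered in the wrong direction; the documents do not establish that. The primary objective, which is to describe outcomes, is unaffected.

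**What to change.** Keep the operated-only tables. For A4091058:

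1. Beside each binary outcome (major procedural complication, post-surgical complication, corrective procedure, dissatisfied at Week 24), add the number of subjects with a replacement and that outcome over all treated subjects in the parent arm, per 1000. Show the replacement rate by arm on the same denominator, as Protocol 9.2 plans, and not on the A4091064 Safety Analysis Set.
2. Show non-enrolled replacements by arm. These can be counted because Protocol 3 and 9.4 send all replacements to adjudication. Footnote that the per-treated rates are lower bounds and that their contrast may be biased if non-enrolment differs by arm. Give a bounding range: with a events, m non-enrolled replacements and N treated, each arm's rate lies between 1000a/N and 1000(a + m)/N. The contrast runs from tanezumab low minus NSAID high to tanezumab high minus NSAID low. Count enrolled subjects with a missing outcome in m.
3. Extend the adjudicated-diagnosis summary to post-surgical complications, as counts by arm because the cells will be small.
4. State in SAP 4.1 that percentages among operated subjects are not a randomised comparison.

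The cost is a few extra rows, using denominators the sponsor already holds, and short wording changes, with no new data collection. The added rates will be imprecise, and outcomes for non-enrollees will remain unknown.
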